5.7.2 Secondary Efficacy Analysis

5.7.2.1 Accelerometer-based upper limb score

For each timepoint, the average score of the two Kinesia ONE assessments will be used for analysis.

For Part A and both phases of Part B, the Kinesia ONE upper limb score will be summarized using descriptive statistics for the reported, change from baseline, and change from randomization (where applicable) values by timepoint. MMRM methods similar to those described in [Section 5.7.1](#) will be used for the change from baseline and change from randomization in Kinesia ONE upper limb scores. Kinesia ONE data will be listed by study part, participant, and visit.

Line-plots of the estimated LS means will be used to graphically illustrate the Kinesia ONE upper limb scores over time.

5.7.2.2 TETRAS combined upper limb score

[figure not shown]
For Part A and both phases of Part B, the TETRAS combined upper limb score as measured by the clinician will be summarized using descriptive statistics for the reported, change from baseline, and change from randomization (where applicable) values by timepoint. MMRM methods similar to those described in [Section 5.7.1](#) will be used for the change from baseline and change from randomization in

TETRAS combined upper limb scores. TETRAS combined upper limb data will be listed by study part, participant, and visit.

Line-plots of the estimated LS means will be used to graphically illustrate the TETRAS combined upper limb scores over time.

5.7.2.3 TETRAS performance subscale total score

For Part A and both phases of Part B, the TETRAS performance subscale total score as measured by the clinician will be summarized using descriptive statistics for the reported, change from baseline, and change from randomization (where applicable) values by timepoint. MMRM methods similar to those described in [Section 5.7.1](#) will be used for the change from baseline and change from randomization in TETRAS performance subscale scores. TETRAS performance subscale data will be listed by study part, participant, and visit.

[figure not shown]

[figure not shown]
5.7.2.5 TETRAS ADL subscale score

In Part B, the TETRAS ADL subscale total score as measured by the clinician will be summarized using descriptive statistics for the reported, change from baseline, and change from randomization (where applicable) values by timepoint. MMRM methods similar to those described in [Section 5.7.1](#) will be used for the change from baseline and change from randomization in TETRAS ADL subscale scores. TETRAS ADL data will be listed by study part, participant, and visit.

5.7.2.6 QUEST total and subscale score

[figure not shown]
[figure not shown]
In Part B, the QUEST total and subscale scores will be summarized using descriptive statistics for the reported, change from baseline, and change from randomization (where applicable) values by timepoint. MMRM methods similar to those described in [Section 5.7.1](#) will be used for the change from baseline and change from randomization in QUEST scores. QUEST data will be listed by study part, participant, and visit.

5.7.3.3 Telehealth Assessments

In Part B, the TETRAS upper limb score as assessed by telehealth will be summarized using descriptive statistics for reported and change from baseline values at Day 41. Telehealth assessment data will not be summarized for the randomized withdrawal analysis set as no telehealth assessments were performed during the randomized withdrawal phase. TETRAS telehealth data will be listed by participant and visit.

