The Screening period for Part A and Part B will be up to 28 days (Day -28 to Day -1). Fourteen additional days (ie, 42 days total) will be allowed in the Screening period for participants who are discontinuing primidone.

Prior to any procedures, participants will provide written informed consent to participate in the clinical trial. Key Screening assessments will include medical history, demographics, physical examination, drug screen, clinical laboratory evaluations and serum pregnancy for women of childbearing potential, 12-lead ECG, vital signs, C-SSRS, assessment of ET severity using the TETRAS Performance subscale (including a video for independent review of eligibility), and a review of concomitant medications. To be eligible, potential participants who are taking prohibited medications will need to successfully discontinue these medications for at least 5 half-lives or 14 days prior (whichever is the longer period of time) before the first dose of study drug.

For those participants requiring the 14 additional days in the Screening period to discontinue primidone, all or some of the Screening assessments may need to be repeated, pending approval by the Sponsor's Medical Monitor.

For participants in **Part A**, following confirmation of eligibility, including review by the Sponsor or designee, participants will complete Baseline assessments (Day 0). Day 0 (Baseline) activities may be combined with Day 1 activities, provided that Baseline activities are completed before dosing and that dosing occurs in the morning of Day 1. In addition, Baseline efficacy assessments should either be conducted on Day 0 or Day 1 pre-dose, but not both to avoid learning effects.

For participants in **Part B**, TETRAS Upper Limb items will also be completed with accelerometry at Screening and via telehealth on Day -2 of the Screening period. The Screening telehealth visit is needed to ensure participants can complete the TETRAS Upper Limb assessment successfully via telehealth and to provide a pre-dose measure. Additional assessments added to Part B screening include TETRAS ADL and [REDACTED]. Following confirmation of eligibility, including review by the Sponsor or designee, participants will complete Baseline assessments (Day 1). Some Baseline assessments (as indicated in Table 3) may be completed on Day -1.

Intervention Period

Part A

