4.1.2.2. Part B

4.1.2.2.1. Open-label Titration Phase

On Day 1, participants will receive a 20 mg dose of PRAX-944 on an empty stomach (at least 1 hour before breakfast). Participants will remain in a clinical setting under medical observation for approximately 6 hours. TETRAS Performance assessments will be performed before dosing and 6 hours (± 2) post-dose.

For dosing on Day 2 through Day 41, participants will be instructed to dose QAM at least 1 hour before breakfast at home.

Participants will continue taking PRAX-944 20 mg QAM at home through Day 3.

On Day 3, participants will receive a telephone call from site staff to inquire about AEs and concomitant medications, confirm dose escalation, and remind the participant about the number of study drug tablets to take on Day 4 through Day 7.

On Day 4, participants will escalate to 40 mg QAM through Day 7, when they will return to the clinic for safety assessments and efficacy testing. On Day 8, participants should escalate to 60 mg QAM through Day 14.

On Day 14, participants will receive a telephone call from site staff to inquire about AEs and concomitant medications, confirm dose escalation, and remind the participant about the number of study drug tablets to take on Day 15 through Day 21.

On Day 15, participants should escalate to 80 mg QAM through Day 21, when they will return to the clinic for safety assessments and efficacy testing. On Day 22, participants should escalate to 100 mg QAM through Day 28.

On Day 28, participants will receive a telephone call from site staff to inquire about AEs and concomitant medications, confirm dose escalation, and remind the participant about the number of study drug tablets to take on Day 29 through Day 42.

On Day 29, participants will escalate to 120 mg QAM through Day 42, when they will return to the clinic for safety assessments and efficacy testing. The dose on Day 42 will be taken in the clinic (see [Section 4.1.2.2.2](#) below).

On Day 35, participants will receive a telephone call from site staff to inquire about AEs and concomitant medications.

On Day 41, participants will complete a TETRAS Performance Upper Limb assessment via a telehealth visit.

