4.1.2.2.2. Double-blind Randomized Withdrawal Phase

[figure not shown]
On Day 42, participants will complete the final clinic visit of the open-label titration phase. Participants will receive their dose of PRAX-944 administered in the clinic on an empty stomach (at least 1 hour before breakfast). Participants will remain in a clinical setting under medical observation for approximately 6 hours. TETRAS Performance assessments will be performed before dosing and 6 hours (± 2) post-dose.

After Day 42, participants will either continue receiving PRAX-944 at their current dose or switch to placebo, depending on their randomization. Randomization in a 1:1 fashion may be completed at any time on Day 37 through 42.

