8.1.1.4. TETRAS Telehealth Assessment

The TETRAS Performance subscale upper limb item (item #4) will be conducted by the site rater using televideo technology while the participant is at home. The purpose of this assessment is to compare upper limb item scores obtained via a telehealth visit to scores obtained in the clinic to assess the reliability of telehealth assessments.

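### No planned output compares telehealth with clinic upper limb scores within participants, although that comparison is the protocol's stated purpose and the paired data are collected

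*SAP*

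**What the plan says.** Protocol 8.1.1.4 gives the telehealth assessment a measurement purpose: "to compare upper limb item scores obtained via a telehealth visit to scores obtained in the clinic to assess the reliability of telehealth assessments". The Synopsis gives the Screening telehealth visit (Day -2) a further role: "to ensure participants can complete the TETRAS Upper Limb assessment successfully via telehealth and to provide a pre-dose measure". Protocol 4.1.2.2.1 schedules the on-treatment visit: "On Day 41, participants will complete a TETRAS Performance Upper Limb assessment via a telehealth visit". The clinic visit on the following day has two ratings. Protocol 4.1.2.2.2 says that "TETRAS Performance assessments will be performed before dosing and 6 hours" (±2) after the dose.

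On analysis, Protocol 9.3.1 names the telehealth score among those to be summarized by time point and tested for change from baseline. SAP 4.9.1.6 defines the score as the sum of the six sub-items and has the date, time and rater recorded. SAP 5.7.3.3 then says that the score "will be summarized using descriptive statistics for reported and change from baseline values at Day 41" and that "TETRAS telehealth data will be listed by participant and visit". SAP 7.1, which records departures from the protocol, does not mention the telehealth comparison.

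**The concern.** Reliability across two modes of assessment is a property of pairs of scores from the same person. A summary of the telehealth scores alone, even set beside a summary of the clinic scores, describes two marginal distributions. It is the same whether the two modes rank and score participants alike or not at all. A reader who sees similar means could take them as evidence that remote rating works, and the planned output would neither support nor contradict that.

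The sample is meant to inform later controlled studies (Protocol 9.1), so the evidence on remote rating may be used. If nobody specifies the pairing now, whoever builds it later from the listings will choose the comparator after seeing the data. A related gap is that SAP 5.7.3.3 does not say which pre-dose score serves as baseline for the Day 41 telehealth change.

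**Working it through.** The documents attach no sample size, precision target, agreement statistic or threshold to telehealth, so there is no planned figure to reproduce. The check sets the schedule against the analysis, then shows what separate summaries leave undetermined.

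**1. Which pairs the schedule supplies** (Protocol Table 3 and footnote e, sections 4.1.2.2.1, 4.1.2.2.2 and 6.6)

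| Telehealth | Clinic | What is fixed | What is not |
|---|---|---|---|
| Day -2, window -2 days | Day 1 pre-dose | Neither follows study drug | Gap of 2 to 4 days (SAP section 4 has no Day 0) |
| Day 41 | Day 42 pre-dose, and 6 (±2) h post-dose | Same dose level, since no dose change is allowed after Day 36 | Time of the Day 41 rating relative to that day's dose |

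The Day 41 dose is taken at home in the morning, so the Day 42 pre-dose rating falls about 24 hours after it. A Day 41 telehealth rating made before that dose resembles Day 42 pre-dose. One made several hours after it resembles Day 42 post-dose. SAP 4.9.1.6 records the telehealth time and SAP 4.8 the administration time, so time since dose can be derived.

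**2. What separate summaries cannot distinguish**

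Assume equal SD in the two modes and correlation ρ (assumed; the documents give neither). Then SD of the difference = SD × √(2(1 − ρ)), and the 95% limits of agreement lie 1.96 × that SD either side of the mean difference.

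| ρ | SD of difference | Limits of agreement |
|---|---|---|
| 0 | 1.414 SD | ±2.77 SD |
| 0.5 | 1.000 SD | ±1.96 SD |
| 0.9 | 0.447 SD | ±0.88 SD |

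The means and SDs by mode are identical in all three rows. In points on the 0 to 24 scale, an assumed SD of the difference of 1, 2 or 3 gives 1.96 × 1 = 2.0, 1.96 × 2 = 3.9 or 1.96 × 3 = 5.9 points either side.

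**3. What a paired analysis could estimate**

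Inputs: about 12 participants in Part B, up to 24 (Protocol 9.1), assuming each contributes a complete pair.

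- 95% CI half-width for the mean difference = t(0.975, n − 1)/√n, in units of the SD of the difference: 0.635 for n = 12 and 0.422 for n = 24. With an assumed SD of 2 points, that is 2 × 0.635 = 1.27 and 2 × 0.422 = 0.84 points.
- 95% CI half-width for each limit of agreement = t × √(1/n + 1.96²/(2(n − 1))): 1.118 and 0.732 SD of the difference.
- One-way ICC, with F = (1 + r)/(1 − r) on n − 1 and n degrees of freedom:

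| Observed ICC (assumed) | 95% CI, n = 12 | 95% CI, n = 24 |
|---|---|---|
| 0.7 | 0.26 to 0.90 | 0.43 to 0.86 |
| 0.8 | 0.46 to 0.94 | 0.60 to 0.91 |
| 0.9 | 0.70 to 0.97 | 0.79 to 0.96 |

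**4. Baseline for telehealth change**

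SAP section 4 takes the latest available value before first dose. Applied to telehealth scores alone, that is Day -2. Applied to the upper limb score regardless of mode, it is Day 1 pre-dose in the clinic, and the Day 41 change then contains any difference between modes as well as the treatment effect. SAP 5.7.3.3 does not say which is meant.

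**The case against.** The strongest reply is that little is lost. All efficacy data are listed by participant with rater ID (SAP 5.7), and with 12 to 24 people every pair can be read off. The planned statistics also include n, SD, median, minimum and maximum, not just a mean. Telehealth is not a listed primary or secondary endpoint, and no visible efficacy or safety conclusion rests on it. The exploratory objectives are blacked out, parts of SAP 5.7.3 are not visible, and table templates are held separately, so an agreement display elsewhere cannot be excluded.

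Much of this stands, and it limits the point. A reader might infer that the trial cannot answer its reliability question. The documents do not support that, because the scores are collected and listed; only the visible planned outputs are silent. A listing is still not a prespecified comparison. SAP 5.7.3.3 also reads as complete and refers to no agreement analysis.

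A reader might also infer that Day 41 telehealth and Day 42 pre-dose clinic are a ready-made matched pair, being one day apart at one dose level. The documents do not support that either, since the Day 41 time relative to dosing is not fixed and a post-dose clinic score exists. Using pre-dose without comment could mix assessment mode with time since dose.

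It is also fair that pairs on different days do not isolate the mode: the differences carry day-to-day tremor variation and repeat-rating error. That calls for a caveat and does not justify leaving the comparison out. The baseline ambiguity is small. The Synopsis gives the Day -2 visit the role of a pre-dose measure, which favours the telehealth reading, and one clarifying phrase settles it.

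**Conclusion.** The point holds as a mismatch between a stated purpose and the prespecified outputs. Following the visible SAP yields no within-participant comparison of telehealth and clinic scores, and SAP 7.1 does not record that the comparison was dropped. The planned summary is compatible with limits of agreement anywhere from ±0.88 SD to ±2.77 SD over assumed correlations of 0.9 to 0. This rests on equal SDs in the two modes, on assumed correlations, and on no agreement analysis lying in text that is not visible.

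The weight is modest. The change is worth making because it is cheap and serves a purpose the protocol states, but with 12 to 24 pairs it will describe agreement and not establish it.

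**What to change.** In SAP 5.7.3.3, add an exploratory paired analysis of telehealth minus clinic upper limb score, reporting n, mean, SD, 95% CI, limits of agreement, and an ICC of named form with its CI, for:

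- (a) Day -2 telehealth against Day 1 pre-dose clinic;
- (b) Day 41 telehealth against Day 42 clinic, with the pre-dose or 6-hour post-dose comparator prespecified by the recorded time since dose of the Day 41 rating, or with both reported.

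State that telehealth change from baseline uses the Day -2 telehealth value, so that mode is not mixed with treatment effect. Label the results exploratory, and note that the differences include day-to-day tremor variation.

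The cost is one paragraph and one table, with no new data. The downside is imprecision, which the reported intervals will make plain.

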5.7.4 Subgroup Analyses

In Part B, subgroup analyses for patients having a baseline TETRAS upper limb score of 10 or higher will be performed for primary and secondary efficacy endpoints, as well as the TETRAS modified total score.

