3.2. Part B

Objective	Endpoint
Primary	

 • To evaluate the safety and tolerability of PRAX-944 in participants with ET 	
 • Incidence and severity of AEs • Changes in vital sign measurements • Changes in clinical laboratory results • Changes in ECG parameters • Incidence of C-SSRS measured suicidal ideation or behavior
Secondary	

 • To evaluate the efficacy of PRAX-944 on upper limb tremor in participants with ET 	
 • Change from Baseline to Day 42 in TETRAS Upper Limb score (bilateral sum of items 4a, 4b, and 4c)

 • To evaluate the efficacy of PRAX-944 on other measures of tremor severity in participants with ET 	
 • Change from Baseline to Day 7 and Day 21 in TETRAS Upper Limb score (bilateral sum of items 4a, 4b, and 4c) • Change from Baseline to Day 7, Day 21, and Day 42 in the following: 
 ○ TETRAS Performance subscale total score ○ Accelerometer-based upper limb score (bilateral sum of items 4a, 4b, and 4c) ○ TETRAS Performance individual item scores

Objective	Endpoint

To evaluate the efficacy of PRAX-944 on measures of disease impact in participants with ET	
Change from Baseline to Day 7, Day 21, and Day 42 in the following:
TETRAS ADL subscale scoreQuality of Life in Essential Tremor Questionnaire (QUEST) total and subscale scores

Exploratory

Objective	Endpoint
	

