5.2. Inclusion Criteria

A participant must meet the following criteria at Screening and Baseline (unless otherwise specified) to be eligible to participate in this clinical trial:

- I 1. Male or non-pregnant, non-lactating female aged 18 years or older.
- I 2. Willing and able to understand and sign an informed consent document indicating that he/she understands the clinical trial purpose, the clinical trial procedures, and that he/she is willing to participate in the clinical trial and comply with the protocol.
- I 3. Body mass index (BMI) at Screening between 18 and 40 kg/m², inclusive.

- I 4. Clinical diagnosis of ET consistent with Movement Disorders Society Criteria, a duration of ET of at least 3 years and with onset before the age of 65.
- I 5. Moderate to severe ET as defined by the following:
- a. A combined bilateral score of ≥ 10 on the TETRAS Upper Limb items 4 a, b, c. (UL tremor severity at Screening will be confirmed by central video review, for eligibility)
OR
 - b. A score of ≥ 2 on 2 or more of the following TETRAS activities of daily living (ADL) subscale items: (2) Feeding with a spoon, (3) Drinking from a glass, (5) Dressing, (6) Pouring, (9) Writing
OR
 - c. A score of ≥ 2 on 1 of the following TETRAS ADL subscale items: (2) Feeding with a spoon, (3) Drinking from a glass, (5) Dressing, (6) Pouring, or (9) Writing AND a score of ≥ 2 on both of the following TETRAS ADL subscale items: (10) Working and (12) Social Impact
- Note: ET severity at Baseline will be confirmed by the Investigator at the clinical trial site.
- I 6. Those currently receiving any medication for their ET must be willing and able to discontinue all but 1 tremor medication and be on a stable dose for at least 28 days.
- I 7. Willing to comply with medically acceptable method of contraception as defined in [Section 5.4.3](#).

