4 DEFINITION OF STUDY VARIABLES

The following definitions will be used throughout the analysis plan for this study:

Study Day

Study day calculations (ex. study day of an event or a visit) will be defined as follows, assuming non-missing dates:

- Study Day = Date of event – Reference date + 1, when the date of interest occurs on or after the reference date;
- Study Day = Date of event – Reference date, when the date of interest occurs before the reference date;

If either date is missing, study day calculations will not be performed.

For this study, the reference date used will be the treatment start date. Based on the calculations above, there will be no study day zero.

Baseline and Change from Baseline

Unless otherwise specified, the baseline value is defined as the last non-missing value collected prior to receiving first dose of study drug. Values collected after the time of treatment start will be excluded from the calculation of baseline as applicable. Post-baseline values will be defined as those collected after the treatment start date (and time, as applicable).

Change from baseline will be defined as: assessment value – baseline value. Change from baseline values will only be derived for post-baseline assessments.

Randomization Baseline and Change from Randomization

The randomization baseline value, used as the reference value for double-blind randomized withdrawal phase efficacy endpoints, is defined as the Day 42 post-dose value. If the Day 42 post-dose value is unavailable, the randomization baseline value will be considered missing.

Change from randomization will be defined as: assessment value – randomization baseline value. Change from randomization values will only be derived for assessments conducted after the randomized treatment start date (and time, as applicable).

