5.7.1 Primary efficacy analysis

For Part A, the change from baseline in TETRAS upper limb score to each post-dose timepoint will be analyzed using Mixed Model Repeated Measures (MMRM) methods using the full analysis set. The model will include timepoint as a fixed effect and the baseline TETRAS upper limb score as a covariate. Within subject variability will be modeled using an unstructured covariance pattern. In case of convergence problems, a banded Toeplitz structure for the covariance pattern will be used. Model based point estimates (ie, least square [LS] means), standard error, 95% confidence interval, and p-value will be reported for each timepoint. Reported p-values will test the LS mean for each timepoint versus zero. Similar MMRM methods will be used for the open-label titration phase of Part B. The SAS code to be used for the MMRM analysis is provided below:

Line-plots of the estimated LS means will be used to graphically illustrate the TETRAS upper limb scores over time.

For Part A and both phases of Part B, the TETRAS upper limb score as measured by the clinician will be summarized using descriptive statistics for the reported, change from baseline, and change from randomization (where applicable) values by timepoint. TETRAS upper limb data will be listed by study part, participant, and visit.

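### The Part B open-label subgroup with upper limb score 10 or higher is chosen on the same Baseline value that is subtracted to form change, which tilts it towards apparent improvement

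*SAP*

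**What the plan says.** For Part B, SAP 5.7.4 plans that "subgroup analyses for patients having a baseline TETRAS upper limb score of 10 or higher will be performed for primary and secondary efficacy endpoints". It names no analysis method. Part B's primary endpoint is safety (Protocol 3.2), so the upper limb change there is a secondary endpoint.

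Under SAP Section 4, "the baseline value is defined as the last non-missing value collected prior to receiving first dose of study drug", which in Part B is normally the Day 1 pre-dose rating. The same section adds: "Change from baseline will be defined as: assessment value – baseline value".

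SAP 5.7.1 sets out a repeated-measures model for Part A and then says: "Similar MMRM methods will be used for the open-label titration phase of Part B". On inference it says "Reported p-values will test the LS mean for each timepoint versus zero", and on adjustment "The model will include timepoint as a fixed effect and the baseline TETRAS upper limb score as a covariate".

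The cut of 10 is also an entry route. Inclusion criterion 5a (Protocol 5.2) requires an upper limb score of at least 10. Routes 5b and 5c admit participants on ADL items instead. The lead-in reads: "A participant must meet the following criteria at Screening and Baseline". SAP 4.9.1.2 and 5.3 classify Baseline as below 10 or at least 10, so participants below the cut are expected.

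**The concern.** A single rating is the participant's usual level plus visit-to-visit error. Keeping only Baseline ratings of 10 or more keeps more upward errors than downward ones. Those errors do not recur at later visits, so the average falls without any treatment. Because Baseline is the value subtracted, the whole of that fall is counted as change.

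With no concurrent control in the open-label phase, nothing offsets it. The Baseline covariate does not help either: within the subgroup, the least-squares mean is evaluated at the subgroup's own, selected, mean Baseline.

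The direction always favours the drug. Protocol 9.1 says the trial is meant to inform later controlled studies, so an inflated change in the more severe participants could feed into their effect-size assumptions.

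**Working it through.** **Inputs from the documents.** The cut of 10 (SAP 5.7.4); change as assessment minus Baseline (SAP Section 4); the test against zero (SAP 5.7.1); about 12 and up to 24 participants in Part B (Protocol 9.1).

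**Assumed, because the documents give no values.** Mean upper limb score 10 to 12, SD 2.5 to 3.5, test-retest reliability r 0.70 to 0.95. Screening, Baseline and on-treatment ratings share one mean and SD, with independent visit errors and no drug effect.

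**The plan's own figure, for scale.** Ten participants, effect size 1.0, about 80% power (SAP 2.3). A paired t-test at two-sided 0.05 (alpha is not stated) gives 80.3%, so the figure reproduces. It makes no allowance for a change that occurs without treatment.

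**Size before any selection at entry.** With a = (10 − mean)/SD,

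expected spurious fall = (1 − r) × SD × φ(a) / [1 − Φ(a)].

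- Central case (mean 11, SD 3, r 0.85): a = −0.333; 0.3774/0.6306 = 0.598; 0.15 × 3 × 0.598 = 0.27 points.
- Largest (mean 10, SD 3.5, r 0.70): a = 0; 0.3989/0.5 = 0.798; 0.30 × 3.5 × 0.798 = 0.84 points.
- Smallest (mean 12, SD 2.5, r 0.95): a = −0.8; 0.2897/0.7881 = 0.368; 0.05 × 2.5 × 0.368 = 0.05 points.

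The SD of change without selection is SD × √[2(1 − r)]. This is 2.71 in the largest case and 0.79 in the smallest, so the fall is 0.31 and 0.06 SD of change.

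**Effect on the test.** Simulated rate of a significant improvement under no drug effect (nominal 2.5%), one post-dose visit, scores rounded to half points, mean 11, SD 3, no selection at entry:

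| r | Enrolled | t-test | With Baseline covariate |
|---|---|---|---|
| 0.85 | 12 | 5.8% | 6.0% |
| 0.85 | 24 | 8.5% | 9.0% |
| 0.70 | 12 | 8.3% | 8.9% |
| 0.70 | 24 | 13.4% | 15.1% |

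**Selection at entry.** Mean spurious change at mean 11, SD 3, r 0.85, half-point scores:

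| Entry assumption | Baseline-defined subgroup | Screening-defined subgroup |
|---|---|---|
| No entry cut on the upper limb score | −0.25 | 0.00 |
| Half qualify by ADL whatever their upper limb score; the rest need 10 or more at both visits | −0.21 | −0.07 |
| Everyone needs 10 or more at both visits | −0.16 | −0.16 |

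In the last row the two subgroups contain the same people. There the mean Screening-to-Baseline change is 0.00, although the later spurious fall is 0.16. For the whole enrolled sample, the spurious change is −0.06 in the second row and −0.16 in the third.

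**The case against.** The case for leaving the plan alone has real weight.

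- **The size is assumed.** The range runs about 17-fold from bottom to top (0.84/0.05), and the low end is negligible. Protocol 8.1.1 asserts good rater reliability but gives no figure. Even 0.31 SD is under a third of the planning effect size of 1.0. This stands: the direction is certain, the size is not.
- **It is a supplementary subgroup** in a small convenience-sample trial. Safety is the primary endpoint of Part B, the full analysis set remains the main efficacy display, and no decision rule uses the subgroup. This stands, and limits how much the point matters.
- **SAP 5.7.4 names no method.** The test against zero is carried over from SAP 5.7.1. This stands; the point about p-values is conditional on it.
- **Severity subgroups by Baseline are conventional.** That is true, but convention does not remove the bias when there is no control arm.
- **Screening has its own drawback.** It can precede withdrawal of primidone or another tremor medication (Protocol 4.1.1; inclusion criterion 6), so it may misplace some participants' severity at the start of treatment. This stands as a cost of the remedy.

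A reader might go further and infer that criterion 5a biases the whole sample equally. The documents do not support that: 5a is one of three alternative routes, and the SAP expects participants below 10. The whole-sample effect therefore depends on the unknown share admitted only by 5a.

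**Conclusion.** The point holds for the Part B open-label change from Baseline in the subgroup scoring 10 or higher. Under the stated assumptions the spurious fall is about 0.05 to 0.84 points before selection at entry. In the central case it is about 0.25 points with half-point scoring, and somewhat less once entry by 5a is allowed for. It shrinks as reliability rises or as the mean Baseline moves above 10.

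Its reach is limited. It is direct for the upper limb, combined upper limb and Performance total scores, which contain item 4. The accelerometer, ADL and QUEST scores are affected only so far as their day-to-day variation is correlated with that of the upper limb rating.

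Three stronger readings are not supported:

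- The randomized withdrawal comparison is not biased between arms by this selection. It takes the Day 42 post-dose value as its reference and has a placebo arm.
- Selecting on Screening does not bring the bias to zero, unless nobody is selected on Baseline at entry.
- A Screening-to-Baseline change near zero would not show that the bias is absent. It can be zero while the later fall persists, and it can also reflect medication withdrawal.

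This is an improvement to consider.

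**What to change.** For the open-label change-from-Baseline analyses, define the SAP 5.7.4 subgroup by the site-rater Screening upper limb score (10 or more versus below 10). Use the same definition in SAP 4.9.1.2 and 5.3 so that the categories match. Alternatively, keep the Baseline-defined subgroup and report the Screening-defined one beside it. In either case, present any Baseline-defined open-label result as descriptive, with no p-value against zero. Add a sentence saying that the Screening definition reduces regression to the mean but leaves some, because participants admitted only by criterion 5a are also selected at Baseline.

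The cost is a phrase in each of three SAP sections and, if both subgroups are shown, one more set of displays. No new data are needed, since the upper limb items are already rated at Screening. A few participants will change subgroup. Because Screening may precede withdrawal of a tremor medication and some Screening assessments may be repeated, the SAP should say which Screening rating counts.
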